4.2.1.2.5 Medically-Attended Adverse Event

An event will be considered as an MAAE if "Yes" is checked for "Is the event an MAAE?" in the CRF. MAAE will be analyzed within 28 days after vaccination, from D29 to 180 days after vaccination, and within 180 days after vaccination.

SAP Core Body: VAP00027

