1.3 Schedule of Activities (SoA)

Visit procedures are detailed in the Operating Guidelines.

Table 1.1: Schedule of activities

Phase III Study, 2 Visits, 2 Phone calls, 1 Vaccination, 2 Blood Samples, 6 Months' Duration Per Participant

Visit/Contact	Collection of information in the case report form (CRF)	Visit 1	Phone Call (PC) 1*	Visit 2	PC2 6-month safety follow-up†
Study timelines (Days)		D01	D09	D29	D181
Time interval (Days)			V01 + 8D	V01 + 28D	V01 + 180D
Time windows (Days)		NA	[+2 D]	[-2, +7 D]	[+14 D]
Visit procedures:					
Informed consent	X	X			
Inclusion/exclusion criteria	X	X			
Collection of demographic data§§	X	X			
Urine pregnancy test (if applicable) ‡		X			
Collection of Medical history (Significant medical history)***	X	X			
Collection of concomitant medications	X Reportable concomitant medication	28 da	ays after vaccinati	on	
History of seasonal influenza vaccination	X	X			
Physical examination§		X		X	
Pre-vaccination temperature		X			

Visit/Contact	Collection of information in the case report form (CRF)	Visit 1	Phone Call (PC) 1*	Visit 2	PC2 6-month safety follow-up†
Study timelines (Days)		D01	D09	D29	D181
Time interval (Days)			V01 + 8D	V01 + 28D	V01 + 180D
Time windows (Days)		NA	[+2 D]	[-2, +7 D]	[+14 D]
Visit procedures:					
Contact Interactive Response Technology (IRT) system for participant number, dose number and randomization to the SN subset	X	X			
Blood sampling (BL) (5 mL)	X	BL0001**		BL0002	
Vaccination (VAC)	X	X			
Immediate surveillance (30 min)	X	X			
Diary card (DC) / electronic DC [eDC] / Memory Aid (MA) provided		DC/eDC		MA	
DC/eDC collected and reviewed				DC/eDC ††	
MA reviewed					MA
Collection of solicited injection site and systemic reactions	X	7 days after	vaccination		
Collection of unsolicited adverse events (AEs)	X	28 days after vaccination		on	
Collection of medically attended AEs (MAAEs)	X	28 days after vaccination		on	
Collection of information on serious adverse events (SAEs), including adverse events of special interest (AESIs)	X	To be reported at any time during the study		ring the study	
Collection of pregnancy	X	To be reported at any time during the study			

Visit/Contact	Collection of information in the case report form (CRF)	Visit 1	Phone Call (PC) 1*	Visit 2	PC2 6-month safety follow-up†
Study timelines (Days)		D01	D09	D29	D181
Time interval (Days)			V01 + 8D	V01 + 28D	V01 + 180D
Time windows (Days)		NA	[+2 D]	[-2, +7 D]	[+14 D]
Visit procedures:					

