2.3.3 Overall Benefit-Risk Conclusion

Considering the measures taken to minimize risk to participants enrolled in this study, the potential risks that may result from study participation are balanced by the anticipated benefits that may be afforded to participants.

3 Objectives and Endpoints

The study objectives and the corresponding endpoints are described in Table 3.1.

Table 3.1: Objectives and endpoints

Objectives	Endpoints
Primary	
To demonstrate the non-inferior hemagglutination inhibition (HAI) immune response of quadrivalent recombinant influenza vaccine (RIV4) for the 4 strains in participants aged 9 to 17 years vs participants aged 18 to 49 years	 Individual HAI titer 28 days after vaccination (D29) Seroconversion (titer < 10 [1/dil] at D01 and post-injection titer ≥ 40 [1/dil] at D29, or titer ≥ 10 [1/dil] at D01 and a ≥ 4-fold rise in titer [1/dil] at D29)
Key Secondary	
To summarize the HAI immune response induced by RIV4 in all participants.	 Individual-HAI titer on D01 and 28 days after vaccination (D29) Detectable HAI titer, ie, with a titer ≥ 10 (1/dil) at D01 and 28 days after vaccination (D29) Individual titer ratio: 28 days after vaccination (D29) /D01 Participants with titer ≥ 40 (1/dil) on D01 and 28 days after vaccination (D29) Seroconversion (titer < 10 [1/dil] at D01 and post-injection titer ≥ 40 (1/dil) at D29 or titer ≥ 10 (1/dil) at D01 and a ≥ 4-fold rise in titer (1/dil) at D29)
To describe the safety profile of RIV4 vaccine in all participants and by age group	Occurrence of any unsolicited systemic adverse events (AEs) reported in the 30 minutes after vaccination Occurrence of solicited (pre-listed in the participant's diary card [DC]/electronic diary card [eDC] and case report book [CRB]) injection site reactions and systemic reactions occurring up to 8 days after vaccination

	 Occurrence of unsolicited AEs up to 28 days after vaccination Occurrence of medically attended adverse events (MAAEs) up to 28 days after vaccination Occurrence of SAEs (including AESIs) throughout the study Occurrence of AESIs throughout the study
Exploratory To describe the neutralizing antibody	Individual seroneutralization (SN)

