8.3.1 Time Period and Frequency for Collecting AE and SAE Information

Immediate Post-vaccination Observation Period

Participants will be kept under observation for 30 minutes after vaccination to ensure their safety. The post-vaccination observation should be documented in the source document.

Reactogenicity

Solicited injection site reactions will be collected from the day of vaccination (D01) until 7 days after vaccination (D08).

Solicited systemic reactions will be collected from the day of vaccination (D01) until 7 days after vaccination (D08).

The solicited injection site reactions and systemic reactions that are pre-listed in the diary cards (DCs)/electronic DCs (eDCs) and CRF, together with the intensity scales, are presented in Appendix 10.2.5.1.1.

Unsolicited Non-serious Adverse Events

Unsolicited non-serious adverse events will be collected from the day of vaccination (D01) until 28 days after vaccination (D29).

The intensity grading scale for unsolicited non-serious adverse events is presented in Appendix 10.2.5.1.2.

Medically Attended Adverse Events (MAAEs)

MAAEs will be collected from the day of vaccination (D01) until 28 days after vaccination (D29).

Adverse Events of Special Interest (AESIs)

AESIs are considered as serious and will be collected from D01 to D181 (6 months).

See Section 8.3.6 for the list of AESIs.

SAEs

Information on SAEs will be collected and assessed throughout the study, from D01 until D181 (6 months after vaccination). However, before the study intervention administration, only SAEs related to study procedures are to be collected in the CRF (eg, SAEs related to blood sampling).

All SAEs will be recorded and reported to the Sponsor or designee immediately and under no circumstance should this exceed 24 hours, as indicated in Appendix 10.2. The investigator will submit any updated SAE data to the Sponsor within 24 hours of it being available.

Investigators are not obligated to actively seek information on AEs or SAEs after conclusion of the study participation. However, if the investigator learns of any SAE, including a death, at any time after a participant has been discharged from the study, and he/she considers the event to be reasonably related to the study intervention or study participation, the investigator must promptly notify the Sponsor.

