8.3.2 Method of Detecting AEs and SAEs

Individual DCs/eDCs, specifically designed for this study by the Sponsor and provided to the study sites, will be given to study participants / parents / legally acceptable representatives for the recording of daily safety information. These DCs/eDCs will include pre-listed terms and intensity scales as well as areas for free text to capture additional safety information or other relevant details. Participants / parents / legally acceptable representatives will also be provided with rulers for measuring the size of injection site reactions, and with standard digital thermometers for measuring daily temperatures. To ensure consistency of reporting, the study sites will instruct participants / parents / legally acceptable representatives on how to correctly use these tools.

At specified intervals, the investigator or a designee will interview the participants / parents / legally acceptable representatives to collect the information recorded in the DC/eDC, and will attempt to clarify anything that is incomplete or unclear. All clinical study information gathered by the study site will be reported electronically by the investigator or designee using a web-based

CRF. Any information that was not documented in the DC/eDC will first be captured in the source document and then reported electronically.

The 6-month follow-up will be done by interviewing participants or parents/legally acceptable representative either during a visit or over the telephone using a questionnaire to capture SAEs and AESIs, if applicable.

Care will be taken not to introduce bias when detecting AEs and/or SAEs. Open-ended and non-leading verbal questioning of the participant is the preferred method to inquire about AE occurrences.

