8.3.7 Medically Attended Adverse Events

MAAEs will be collected using the same process as other AEs. See Appendix 10.2.1 for definition of MAAEs.

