4.2.4.3 Duration of the Study

The duration of the study is computed in days as follows:

• Maximum (Visit dates, Termination date, safety follow-up date) – minimum (V01 date) + 1

The duration of the active phase of the study is computed in days as follows:

• Maximum (latest date of V02, latest date of termination during the active phase) – minimum (V01 date) + 1,

The duration of the D181 safety follow-up phase of the study is computed in days as follows:

• Maximum (date of D181 safety follow-up) – minimum (V02 dates, termination dates during the active phase) + 1.

5 Changes in the Conduct of the Trial or Planned Analyses

All analyses planned to be conducted after the interim analysis defined in section 3.5 are strictly descriptive.

SAP Core Body: VAP00027

If the study Team decides not to conduct this interim analysis as defined in section 3.5 and proceed with the completion of the collection of all safety (6 month-follow-up) data through the end of the study; no amendment of this SAP will be written regarding the non-conduct of this interim analysis (section 3.5).

This decision by the study Team would not affect the primary objective of this study and would not require an amendment of characteristics of any of the analyses defined and planned in this study, such as an adjustment of type I and type II errors.

Discarding the interim analysis at D29 from this study, will be reported in only the protocol amendment, and no amendment of this SAP will be written regarding the non-conduct of this interim analysis.

Additionally, blood visit window is increased at statistical analysis level to address operational constraints whilst maintaining clinical relevance of the immunology read-outs.

Moreover, the recruitment of children and adolescents from 9 to 17 years was revealed harder than the recruitment of adults from 18 to 49 years. Hence, the last adult was enrolled on January, 5th 2023, whereas last participant from 9 to 17 years was enrolled on April, 28th 2023.

To assess the impact of this delay in recruitment of participants from both age groups, a complementary analysis will be performed by describing the main immunogenicity endpoints in the period where participants from both age groups were enrolled (i.e., with all participants with D01 date until January, 5th 2023).

SAP Core Body: VAP00027

6 Supporting Documentation

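### The SAP plans analyses of medically attended adverse events to 180 days, but their collection is planned only to D29 and the endpoint stops at 28 days

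*SAP*

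**What the plan says.** SAP 4.2.1.2.5 identifies an MAAE by a CRF checkbox and sets three analysis windows: "MAAE will be analyzed within 28 days after vaccination, from D29 to 180 days after vaccination, and within 180 days after vaccination". SAP 4.2.1.2.6 and 4.2.1.2.7 set the same three windows for SAEs and AESIs.

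The statements on MAAE timing elsewhere stop at 28 days:

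- Protocol 8.3.1, on collection: "MAAEs will be collected from the day of vaccination (D01) until 28 days after vaccination (D29").
- Protocol Table 1.1 and SAP Table 1.2: the MAAE collection row is marked as 28 days after vaccination. SAP Table 1.2 is headed as modified from the protocol, yet it keeps this period.
- Protocol Table 3.1 and SAP Table 2.1, on the endpoint: "Occurrence of medically attended adverse events (MAAEs) up to 28 days after vaccination".
- Protocol 8.3.7: "MAAEs will be collected using the same process as other AEs". For those other events, protocol 8.3.1 says: "Unsolicited non-serious adverse events will be collected from the day of vaccination (D01) until 28 days after vaccination (D29").

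For the 6-month contact, protocol 8.3.2 describes an interview at a visit or "over the telephone using a questionnaire to capture SAEs and AESIs, if applicable". MAAEs are not named.

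SAP section 5, which lists changes to conduct and planned analyses, notes that the "blood visit window is increased at statistical analysis level". It says nothing about longer MAAE collection.

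**The concern.** An analysis window should not run past the period in which the event is collected. SAEs and AESIs are collected to D181, so the three windows suit them. MAAEs are not, yet the SAP gives them the same windows. The shared wording suggests it was carried across, although the documents do not say so.

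The denominator makes the gap matter. For unsolicited AEs, SAP 3.4.3 uses all vaccinated participants. If a 180-day MAAE table follows that rule, a participant whose late medical visit was never asked about counts as having had no event. The table would carry a 6-month label while planned collection of non-serious MAAEs covers about the first month, in a study meant to support extension of the vaccine to a pediatric population. A low late frequency could be read as reassurance when it reflects lack of collection.

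**Working it through.** The plan gives no figure to reproduce. The check compares passages and counts days.

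**Day numbering.** SAP 4.2.1.2.3 defines study day as event date minus vaccination date plus 1. So 28 days after vaccination is D29 and 180 days after is D181, in agreement with both schedules.

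| Item | Period | Source |
|---|---|---|
| MAAE collection | D01-D29 | Protocol 8.3.1, Table 1.1; SAP Table 1.2 |
| MAAE endpoint | up to 28 days | Protocol Table 3.1; SAP Table 2.1 |
| Non-serious unsolicited AE collection | D01-D29 | Protocol 8.3.1 |
| SAE and AESI collection | D01-D181 | Protocol 8.3.1 |
| MAAE analysis | to D29; D29-D181; to D181 | SAP 4.2.1.2.5 |

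**The 180-day window.** It spans 181 study days, and planned MAAE collection covers 29. Uncovered: 181 − 29 = 152 days (D30-D181), and 152/181 = 84.0%.

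**The D29-to-180-days window.** It spans 181 − 28 = 153 days. Only D29 lies within planned collection, so 152/153 = 99.3% is uncovered.

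**Allowing for a late Visit 2.** The visit window is −2 to +7 days around D29, so the latest in-window visit is D36. If every MAAE up to that visit were reported there, D37-D181 would remain: 181 − 36 = 145 days, and 145/181 = 80.1%. Using D39 instead, the upper limit of the per-protocol blood-sample window in SAP 3.3, gives 181 − 39 = 142 days, and 142/181 = 78.5%.

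**Conflict within the SAP.** Protocol 10.2.1 excludes solicited reactions from MAAEs, and SAP 4.2.1.2.5 sits under the heading for unsolicited AEs. SAP 4.2.1.2.3 keeps unsolicited AEs with onset after D29 out of the analysis and sends them to a separate listing. A non-serious MAAE starting on D60 would go to a listing under 4.2.1.2.3 and into a table under 4.2.1.2.5.

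**Overlap.** SAP 4.2.1.2.3 treats within 28 days as D01-D29, so D29 falls in both the first and second MAAE windows.

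**The case against.** The strongest case on the other side has four parts.

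1. *Late MAAEs are not wholly uncollected.* An event after D29 that is also an SAE or AESI is collected to D181 and could have the MAAE box checked. This stands: the later windows need not be empty. But they would then hold mainly that subset, which is not an MAAE frequency. The day percentages above describe planned collection of MAAEs as such; the firm gap is for MAAEs that are neither serious nor AESIs.

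2. *The capture tools are not available.* The 6-month questionnaire and the memory aid handed out at Visit 2 are not in the documents and might ask about medical visits. This also stands, so the inconsistency is certain and the incomplete frequency is inferred from the described procedures. If those tools did collect MAAEs, the collection period, schedules and endpoint tables would still need reconciling with the analysis.

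3. *SAP 4.2.1.2.3 already keeps late non-serious events out of the tables.* On that reading the late windows hold only the serious or AESI subset, but they are not labelled so. On the other reading the two SAP sections contradict each other. Either way 4.2.1.2.5 needs correction.

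4. *The percentages are calendar ratios, not an effect size.* Correct. They show how far the label exceeds planned collection and say nothing about how many events would be missed.

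**Conclusion.** The concern holds. SAP 4.2.1.2.5 plans MAAE frequencies over D01-D181, but planned MAAE collection and the endpoint definition end at D29, and no text in either document reconciles the two. By day count, 152 of 181 days (84.0%) lack planned MAAE collection, or 145 of 181 (80.1%) if full capture to the latest scheduled Visit 2 is allowed. How many events would be missed cannot be stated, because the documents give no MAAE rate.

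This rests on the collection periods as written and on the 6-month questionnaire covering what protocol 8.3.2 says it covers. Severity is minor: the output is descriptive, the protocol-defined 28-day analysis remains, and the non-inferiority tests, type I error and power are unaffected.

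**What to change.** Preferred: reword SAP 4.2.1.2.5 so that MAAEs are analyzed within 28 days after vaccination (D01-D29), and delete the two later windows. This also removes the clash with SAP 4.2.1.2.3 and the double use of D29 for MAAEs.

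Alternative: keep the later windows only if they are restricted to, and labelled as, events captured through SAE or AESI reporting. Late non-serious events, such as those reported at a Visit 2 held after D29, would then go to the listing that SAP 4.2.1.2.3 already provides.

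If MAAEs were in fact collected after D29, reconcile the protocol, SAP Tables 1.2 and 2.1 and SAP 4.2.1.2.3 with that, and record the change in SAP section 5.

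The cost is one sentence or one table label. Deletion means that no 6-month MAAE frequency is reported, but the documents plan no collection that would support one.

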4.2.1.2.6 Serious Adverse Events

An event will be considered as a serious event if "Yes" is checked for "Serious" in the CRF.

SAEs will be analyzed within 28 days after vaccination, from D29 to 180 days after vaccination, and within 180 days after vaccination.

4.2.1.2.7 Adverse Events of Special Interest

An event will be considered as an AESI if "Yes' is checked for "Is the event an AESI?" in the CRF.

AESIs will be analyzed within 28 days after vaccination, from D29 to 180 days after vaccination, and within 180 days after vaccination.

4.2.2 Other Safety Endpoints

4.2.2.1 Pregnancy

This information will be summarized as collected. No derivation or imputation will be done.

4.2.2.2 Action Taken

This information will be summarized as collected, including missing observations. No derivation or imputation will be done.

4.2.2.3 Seriousness

This information will be summarized as collected. No derivation or imputation will be done.

4.2.2.4 Outcome

This information will be summarized as collected. No derivation or imputation will be done.

4.2.2.5 Causal Relationship

This information will be summarized as collected in the field "Relationship to study vaccine". Missing causal relationship will be handled as described in Section 3.4.4.1.2. Relationship to study procedure is only presented in the listing.

4.2.2.6 Adverse Events Leading to Study Discontinuation

This information will be summarized as collected. A flag is available in the clinical database for all AEs in order to identify AEs leading to discontinuation before the end of active phase.

SAP Core Body: VAP00027

In general, the items that are counted are:

- Disposition table: A participant who, on the "Completion at End of Active Phase" form question "What was the participant's status?" has "Adverse Event" checked.
- Safety overview table: A participant who has either on the "Completion at End of Active Phase" form, question" What was the participant's status?" has "Adverse Event" checked or lists a solicited AE that has "Caused Study Termination" checked that is at least Grade 1 or an unsolicited AE that has "Caused Study Discontinuation" checked that is at least Grade 1 or missing and is within the time period indicated.
- System Organ Class (SOC)/Preferred Term (PT) table: A solicited AE that has "Caused Study Termination" checked that is at least Grade 1 or an unsolicited AE that has "Caused Study Discontinuation" checked that is at least Grade 1 or missing and is within the time period indicated.

4.2.3 Immunogenicity

4.2.3.1 Computed Values for Analysis

For the derivation of immunogenicity endpoints, all values strictly under the lower limit of quantification (LLOQ) will be treated as LLOQ/2, and all values above or equal to the upper limit of quantification (ULOQ) will be treated as ULOQ.

For the analysis of the results of HAI assay which is performed in duplicate, the individual geometric mean (GM) of both values will be computed for each blood sample and each strain, after managing extreme values as described above. The computed value is then considered the titer for that particular blood sample.

Unique records will be recorded for SN titration.

4.2.3.2 Fold-rise

For the HAI immune response, the derived endpoint fold-rise is driven by both baseline (D01) and post-baseline (D29) computed values as described in Section 4.2.3.1 and is computed as individual ratio:

• 28 days after vaccination divided by D01.

Note: if pre-vaccination (D01) or post-vaccination (D29) values is missing, the fold-rise is missing.

4.2.3.3 Seroconversion

For HAI assay, SC is defined as a binary indicator. If a pre-vaccination (D01) titer < 10 (1/dil): post-vaccination titer ≥ 40 (1/dil) on 28 days after vaccination (D29), or ≥ 4 -fold-rise for participants with a pre-vaccination titer ≥ 10 (1/dil), the derived SC indicator will be "Yes", otherwise will be "No".

SAP Core Body: VAP00027

Note: if pre-vaccination (D01) or post-vaccination (D29) value is missing, the SC is missing.

4.2.4 Derived Other Variables

4.2.4.1 Age for Demographics

The age of a participant in the study will be the calendar age in years at the time of inclusion, as collected in the eCRF.

The study group will be determined by the investigator:

- If the participant is between the age of 9 and 17 years at the time of inclusion; the participant will be assigned to study age group 9-17 years, otherwise;
- If the participant is between the age of 18 and 49 years at the time of inclusion; the participant will be assigned to study age group 18-49 years.

4.2.4.2 Duration of a Participant in the Trial

The duration of a participant in the trial, including the D181 safety follow-up, is computed as follows:

• Maximum (visit dates, termination date, safety follow-up date) – V01 date + 1.

The duration of a subject in the active phase of the trial is computed as follows:

• Maximum (V02 dates, termination date) – V01 date + 1.

